### 1.2.4 Inclusion Criteria

Patients will be included in the study based on the following criteria:

- Good understanding in written and verbal English;
- Able to give informed consent;
- 40-85 years old inclusive;
- Have two or more chronic conditions (see *table1* in MAP protocol v6;20.6.2018)
- Have access to a mobile phone for use in potential study activities;
- Able to walk independently;

There are no limitations with disease duration, medication use and/or initiation of new treatment unless there are specific recommendation for bed rest and minimising physical activity for a specific condition.

### **1.2.5** Exclusion Criteria

Patients with following will be excluded:

- Patients with limited understanding of written and verbal English;
- Patients with: dementia, learning disability, mental health disorders other than depression, epilepsy;
- Patients in palliative care;
- Pregnancy;
- Patients currently participating or participated in another interventional trial in the previous 12 weeks;
- Patients with frailty. The definition of frailty will be at the investigator's discretion and based on patients:
  - Living in care homes or institutions;
  - Having daily support for daily activities such as washing, cooking, household tasks etc;
  - Having had unintentional significant weight loss in the last 3-6 months;
  - Having BMI less than 18.5 kg/cm^2

### **1.2.6** Sample size calculations

The primary outcome is change from baseline to 12 months average daily physical activity, as quantified by the Euclidean norm minus one (ENMO) method measured in milligravity units (mg). This is the main measure of activity derived from the activity monitor. In order to detect a minimum clinically significant difference of 2.1 mg, which is equivalent to an overall increase in physical activity volume of approximately 30 minutes of light walking at 4km/h, assuming a standard deviation of 5.3 mg [1], a power of 80% and significance level of 5%, the sample size requires 202 participants. To allow for 20% loss to follow-up and 20% non-compliance of the activity monitor, we will therefore need to recruit 338 participants (169 in each group).

# 2 Outcome Measures

### 2.1 Primary outcome measures

The primary outcome measure is change in overall volume of physical activity measured using accelerometer between baseline and 12 months.

A complete case population will be used for the primary analysis. This will be followed by sensitivity analyses which will include an intention to treat (ITT) population by imputing missing data to assess the robustness of the findings to missing data.

### **2.2** Secondary outcome measures

Below is a list of all of the secondary outcomes collected at baseline and 12 months.

#### Ambulatory activity:

Patients will be asked to wear an accelerometer 24 hours/day for up to eight days to record total volume of physical activity, which includes light, moderate, vigorous and moderate to vigorous physical activities (MVPA).

Anthropometric measures:

- Weight
- Body mass index (kg/m^2)
- Waist circumference (cm)
- Hip circumference (cm)
- Waist to hip ratio

#### Clinical data:

- Blood pressure (mmHg)
- Muscle strength (measured by dynamometer)
- Resting heart rate (bpm)
- Total cholesterol (mmol/l)
- HDL cholesterol (mmol/l)
- LDL cholesterol (mmol/l)
- Kidney function (sodium, potassium, urea, creatinine and eGFR)
- HbA1c (mmol/mol, %)
- Medical history, details of any history of disease

#### **Questionnaire Measures**

A number of different questionnaire measures will be completed by participants at baseline and 12 months. Details of these questionnaire measures are as follows:

- i. Lifestyle behaviours (self-reported): measured by dietary questions, sleeping pattern, smoking status and physical activity measured by RPAQ;
- ii. Medication adherence: measured by ASK-12 (Adherence Starts with Knowledge (12 items survey)
- iii. Quality of life: measured by EQ-5D-5;
- iv. Psychological health, i.e. depression and anxiety: measured by HADS;
- v. Chronic Disease Self-Efficacy: measured by Managing Chronic Disease Scale;
- vi. Self-efficacy for exercise: measured by Self-Efficacy for Exercise (SEE) Scale;

#### Smoking status, sleeping behaviours

No attempt will be made to impute the missing values for the secondary endpoints.

# **3** Analysis Sets/Populations

### 3.1 Missing values and outliers

Missing values represent a potential source of bias in clinical trials. Therefore, every effort will be made to ensure the data is fully explored for potential problems and have been correctly entered into the database. Participants who did not attend the baseline assessment after consent will be excluded from all analyses, but will be noted on the CONSORT flow chart. For the primary and secondary analyses, participants who do not have an outcome measurement will be excluded; as discussed in section 3.2. Sensitivity analyses will be performed to assess the robustness of the findings to missing data. Outliers will be identified by examining graph plots such as normality plots, box plots and histograms. Values that visually appear outside of the main distribution (i.e. outliers) will be further investigated and if this is the correct observation it will remain in the analysis, however further assumptions will be made to assess possible influences on the results using a sensitivity analysis; by removing the outlier or outliers to compare results. Where results from the two analyses are discrepant, this fact will be reported and discussed in the study publication.

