### 1.2.2 Randomisation

Participants will be randomised 1:1; stratified by gender (male; female) and ethnicity (White European; other) to either intervention or control groups.

If two people are taking part from the same household they will be randomised to the same arm to prevent contamination taking place.

Both control and intervention participants will be informed of the outcome of the randomisation. In addition intervention participants will be sent a letter confirming the date and the venue of the education sessions.

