# **4** General Issues for Statistical Analysis

### 4.1 Multiplicity, Multiple Comparisons and Interim Analyses

All tests and reported p-values will be two-sided, where a p-value of < 0.05 will be considered to be statistically significant. Estimates will be presented with 95% confidence intervals. There will be no formal adjustment for multiple significance testing. The outcomes however, are clearly categorised by the degree of importance (primary and secondary). No formal interim analyses were planned.

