#### 4.5.2.2 Intention-to-treat Population

To allow for full analysis set, missing data will be imputed using a multiple imputation procedure which substitutes predicted values from a regression equation. The imputation will be carried out by the MI command in Stata . MI replaces missing values with multiple sets of simulated values to complete the data, performs standard analysis on each completed dataset, and adjusts the obtained parameter estimates for missing-data uncertainty using Rubin's rules to combine estimates .

The following procedure will be followed:

- The MI will be set as wide
- The MI will register imputation of the overall volume of physical activity at 12 months and at baseline
- A regression method will be used , where the registered variables will be individually adjusted for the randomisation and stratification factors (sex and ethnicity), with 100 imputations to avoid biased estimates, rseed (2259) and the force options
- MI estimate will provide the final results using the same regression model as the primary analysis and covariate adjustments.

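### The SAP's only check on missing outcomes makes the same kind of assumption as the primary analysis, so no planned analysis tests dropout that depends on activity itself

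*SAP*

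**What the plan says.** On the primary analysis, SAP section 2.1 states: "A complete case population will be used for the primary analysis". Sections 3.1 and 3.2 confirm that anyone without the outcome is left out. Section 3.1 treats missing values as a possible source of bias and says: "Sensitivity analyses will be performed to assess the robustness of the findings to missing data".

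Sections 2.1 and 3.3 make imputation under intention to treat that check, and section 4.5.2.2 specifies it: "missing data will be imputed using a multiple imputation procedure which substitutes predicted values from a regression equation". The variables imputed are activity volume at baseline and at 12 months. The predictors named are randomised group, sex and ethnicity. The primary model in section 4.5.1 also adjusts for baseline activity and for change in wear time.

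On the amount of missing data, section 1.2.6 inflates the sample size "To allow for 20% loss to follow-up and 20% non-compliance of the activity monitor".

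The other planned analyses do not address the question. The per-protocol set (3.4) again requires complete outcome data. The analyses by sessions attended and by stratum (4.5.2.3, 4.5.2.4) reuse the primary model. The outlier analysis in 3.1 concerns observed values.

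**The concern.** Complete-case regression is unbiased if, given the covariates in the model, whether the outcome is missing is unrelated to its value. Multiple imputation from a regression with no shift makes the same kind of assumption, given the predictors in the imputation model. The SAP does not name this assumption; it follows from the methods chosen. No delta-adjusted, pattern-mixture, reference-based or tipping-point analysis appears.

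The doubt matters because participants know their allocation (section 1.2.2) and the outcome exists only for those who return and wear a monitor. Activity could plausibly influence both. This is an inference from the design; the SAP gives no data on it. The bias could run either way:

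- If less active intervention participants are the ones lost, the complete-case analysis overstates benefit.
- If less active controls are the ones lost, it understates benefit.
- If departures and missing shares are equal in both arms, they cancel.

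At stake is what the trial can say about robustness. Agreement between the two planned analyses would not be evidence against outcome-dependent dropout, and disagreement could simply reflect their different covariates.

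**Working it through.** **Inputs (SAP).** Section 1.2.6 gives the target difference ("In order to detect a minimum clinically significant difference of 2.1 mg"), an SD of 5.3 mg, and the power and size ("a power of 80% and significance level of 5%, the sample size requires 202 participants"). Section 4.1: "All tests and reported p-values will be two-sided". Section 1.2.2: "Participants will be randomised 1:1". Recruitment is 338, or 169 per arm.

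**Step 1: reproduce the plan's figures.** A two-sided t-test calculation with difference 2.1, SD 5.3, alpha 0.05 and power 0.80 gives 100.96, so 101 per arm and 202 in total. This matches the plan.

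- Adding the two allowances: 101 / (1 − 0.40) = 168.3, so 169 per arm and 338 in total. This matches.
- Multiplying them: 101 / (0.8 × 0.8) = 157.8, so 158 per arm and 316 in total. This does not match.

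The plan therefore allows for 338 − 202 = 136 participants without the primary outcome, and 136 / 338 = 40.2%.

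**Step 2: how large a departure changes the conclusion.** Assume an observed effect of 2.1 mg and the same missing share m in each arm. Let D be how much further below their assumed values the intervention non-responders lie than the control non-responders. Then:

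- overall effect = 2.1 − m × D
- SE = 5.3 × √(2 / n per arm), held at its complete-case value as D varies
- the lower 95% limit reaches 0 at D = (2.1 − 1.96 × SE) / m
- the estimate reaches 0 at D = 2.1 / m

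| | 40.2% missing | 20% missing |
|---|---|---|
| Analysed (per arm) | 202 (101) | about 270 (135) |
| SE | 5.3 × √(2/101) = 0.746 | 5.3 × √(2/135) = 0.645 |
| 95% CI at 2.1 mg | 0.64 to 3.56 | 0.84 to 3.36 |
| D at which significance is lost | 0.638 / 0.402 = 1.6 mg (0.30 SD) | 0.836 / 0.20 = 4.2 mg (0.79 SD) |
| D at which the effect is 0 | 2.1 / 0.402 = 5.2 mg (0.98 SD) | 2.1 / 0.20 = 10.5 mg (1.98 SD) |

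**Step 3: would the planned imputation show the problem?** An illustrative simulation used these assumptions: true effect 0; 169 per arm; change SD 5.3 mg; baseline to 12-month correlation 0.7; about 40% missing; missingness at random in controls, and rising in the intervention arm by 0.10 to 0.25 log-odds per mg of worse change. Baseline was fully observed. Sex, ethnicity and wear time were left out. The imputation model contained arm but not baseline activity.

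- Missingness unrelated to outcome: both analyses are essentially unbiased (0.02 and −0.004 mg).
- Missingness related to outcome: the complete-case estimate is biased by +0.9 to +1.9 mg, and the imputed estimate by +0.6 to +1.1 mg.

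The two analyses differ, but both remain biased in the same direction. Placing the dependence in the control arm instead would reverse the sign.

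**Step 4: the imputation model as written.** Section 4.5.2.2 does not name baseline activity as a predictor of 12-month activity. It does not register change in wear time, which the final model uses. Read literally, participants without 12-month monitor data would still lack that covariate, and the imputed analysis could fall back to nearly the complete cases. This must be settled before any shift is applied.

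**The case against.** The strongest case against has four parts.

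- **The 40% is an allowance, not a forecast.** This stands. A reader might infer that 40% missing is expected, but section 1.2.6 only makes provision for it. Section 4.3 accepts one valid day of monitor data, a lenient rule that may keep monitor non-compliance below 20%. With 20% missing the result is much harder to overturn.
- **The two analyses need not agree.** This stands. A reader might infer that complete-case analysis and imputation give nearly the same answer by construction. The documents do not support that: baseline activity is also imputed, and the imputation model omits two covariates of the primary model. The simulation shows different results. But a difference arising from unlike models is not a test of outcome-dependent dropout.
- **The mechanism is assumed, and 1.6 mg is not small.** This stands in part. Nothing in the SAP shows who will drop out, so a reader should not infer that benefit will be overstated. A departure of 1.6 mg is 76% of the target difference (1.6 / 2.1) and must be a difference between arms. Not knowing the mechanism is, however, the reason to vary the assumption.
- **The SAP makes no false claim.** This also stands. It says that imputation will assess robustness, not that it will establish robustness to every form of dropout. The finding is a gap, not a contradiction.

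**Conclusion.** The gap is real. The SAP sets out to assess robustness to missing data, and every analysis it specifies leaves unvaried the assumption that missingness does not depend on unobserved activity. With the roughly 40% missing that the sample size provides for, and an observed effect equal to the 2.1 mg target, a between-arm departure of about 1.6 mg among non-responders removes significance and about 5.2 mg removes the effect. With 20% missing the figures are about 4.2 mg and 10.5 mg.

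These are illustrations. They assume equal missing shares in the two arms, an SD of 5.3 mg, and an SE that does not change with the shift. They do not show that the primary analysis is biased, or in which direction. The planned primary analysis can stand. What is missing is an inexpensive analysis that should be added, because it decides what the trial can claim about robustness.

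**What to change.** In SAP section 4.5.2.2:

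1. Align the imputation model with the primary model: include baseline activity as a predictor of 12-month activity, and bring change in wear time into the imputation.
2. Add a delta-adjusted (pattern-mixture) analysis that shifts imputed 12-month activity independently in each arm over a two-way grid. Shifting only the control arm downwards would increase an observed benefit, and equal shifts with equal missingness would roughly cancel, so the full grid is needed.
3. Make the grid wide enough to reach both the point where the 95% CI includes 0 and the point where the estimate is 0. At 40% missing, 0 to −6 mg does this (2.1 − 0.402 × 6 = −0.3 mg). With less missing data it must be wider: beyond −10.5 mg at 20%.
4. Report both tipping points and judge whether departures of that size are plausible.
5. State in sections 3.1 to 3.3 that the complete-case and standard imputed analyses assume data missing at random given their covariates.

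The cost is a few lines of imputation code and one figure or table. No new data are needed and the primary analysis keeps its form. The downside is slightly more work and results that may look less certain. Section 1 allows the SAP to be amended before database lock; after lock, the same analysis can be reported as post hoc.

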# 3.2 Complete Case Population

The level of missing data for each outcome will be assessed. If missing outcome data is present the initial analysis will be based on the complete cases. All tests of the effect of treatment on outcomes will be conducted on a complete case (CC) population. That is, all the recruited participants will be included in the analysis, with the exception of those with missing outcome data. This will be done on a 'by analysis' basis, i.e. only those participants with missing data for variables required for a specific analysis will be removed.

# 3.3 Intention-to-treat Population/Full analysis set

The intention-to-treat (ITT) analysis population will consist of all participants randomised. Participants will be analysed in the group to which they were randomly allocated and regardless of any protocol deviations or violations. Multiple imputation methods will be used to impute missing outcome data. This will be a sensitivity analysis.

# 3.4 Per-protocol Population

The per protocol (PP) population are those who were compliant with the protocol and have complete data for the analysis concerned on 'by analysis' basis. In the control arm, the PP population will include all participants randomised to that arm with complete outcome data. In the intervention arm, the PP population will be defined as participants who have attended at least one group session of the programme and have outcome with complete data. This will be a sensitivity analysis.

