### **1.2.3 Study treatment interventions**

This will be a randomised control trial with an intervention group and a control group.

1) Intervention group: Those randomised to the intervention group will be invited to attend four patient-centred education sessions of the structured education programme and to receive regular reminders with Short Message Service (SMS) messages (text messages) after the first session. The programme focuses on promotion of personalised physical activity and health-related self-management activities, which impact on quality of life.

These structured education sessions have been developed during an iterative process in conjunction with PPI work and other stakeholders through the use of existing infrastructure consisting of Diabetes Education and Self-Management in on-going and Newly Diagnosed (DESMOND) groups and a network of trained facilitators.

2) Control group: No change in the usual care of these participants will take place and they will continue with their routine care management in line with their direct care team's current recommendations for people with multimorbidity.

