# 4.5 Primary Endpoint Analysis

### 4.5.1 Primary Analysis of Primary Endpoints

The primary outcome is change in overall volume of physical activity (average acceleration, ENMO) from baseline to 12 months. For the primary outcome treatment arm will be compared using linear regression modelling with

1. a binary indicator for randomisation group as the explanatory variable

2. terms for stratification factors (gender and ethnicity) as confounders

3. adjustment for the change from baseline in accelerometer wear time and baseline overall volume of physical activity.

The primary analysis at 12 months will be based on complete data.

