### 4.5.2 Sensitivity Analyses

#### 4.5.2.1 Per Protocol Population

For the PP analysis, participants who have engaged with at least one group session of the programme will be included. The PP will adhere to the same steps as the primary analysis.

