#### 4.5.2.3 Exploratory analysis of number of sessions attended

We will assess the effect of the number of sessions attended on the primary and secondary outcomes of the physical activity using the same model used in the primary analysis. We will assess three alternative scenarios

- I. <1, no sessions attended
- II. 1-3 sessions attended
- III. All 4 sessions attended

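### The per-protocol set filters only the intervention arm on attendance, and the sessions analysis has no stated reference group; both are open to selection bias, and a CACE analysis should be added

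*SAP*

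**What the plan says.** Section 3.4 of the SAP defines the per-protocol set differently in the two arms. For the intervention arm: "In the intervention arm, the PP population will be defined as participants who have attended at least one group session of the programme", together with complete outcome data. For the control arm: "In the control arm, the PP population will include all participants randomised to that arm with complete outcome data". Section 3.4 gives the status of this analysis as "This will be a sensitivity analysis". Section 4.5.2.1 repeats the attendance rule ("participants who have engaged with at least one group session of the programme will be included") and fixes the model: "The PP will adhere to the same steps as the primary analysis".

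That model, in section 4.5.1, contains randomised group, gender, ethnicity and "adjustment for the change from baseline in accelerometer wear time and baseline overall volume of physical activity".

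Section 4.5.2.3, headed as exploratory but placed under Sensitivity Analyses, states: "We will assess the effect of the number of sessions attended on the primary and secondary outcomes of the physical activity". It uses the primary model and lists three levels: none, one to three, and all four sessions. It names no reference group and does not say how controls enter.

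No section plans an instrumental-variable analysis or any other allowance for selection into attendance.

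**The concern.** Randomisation balances would-be attenders and would-be non-attenders between the arms. The per-protocol rule undoes this by removing non-attenders where they can be seen (intervention) and leaving their counterparts where they cannot (control). If people who turn up would have changed their activity differently anyway, that difference enters the estimate as if it were a programme effect. None of the model covariates measures willingness to attend. Exercise self-efficacy is collected at baseline (section 2.2) but is not in the model.

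The sessions analysis has the same weakness and a specification gap as well. With no reference group fixed, several different contrasts fit the text, and they can give quite different answers from the same data.

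What is at stake is interpretation. Analyses listed as sensitivity analyses tend to be read as showing whether the main result is robust, and section 4.1 applies the 5% threshold to all tests without multiplicity adjustment. A comparison that may lean towards the programme is poorly suited to that use.

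**Working it through.** **The plan's own figures (section 1.2.6).** Difference 2.1 mg, SD 5.3 mg, 80% power, two-sided 5%. The t-based calculation gives 100.96, so 101 per arm and 202 in total, as stated. Inflation: 202 / (1 − 0.40) = 336.7, which becomes 338 (169 per arm), also as stated. The standard error of a two-arm difference with 101 per arm is 5.3 × √(2/101) = 0.746 mg.

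**Bias of the per-protocol estimate.** Notation:
- p: share who attend no session (not in the SAP; assumed)
- d: difference in mean change without the programme, would-be attenders minus non-attenders, after covariate adjustment (not in the SAP; assumed)
- τ: effect of the programme on attenders
- a: mean untreated change in would-be attenders

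Assume that allocation has no effect on non-attenders and that controls have no access to the programme. Set missing outcomes aside. Then:
- Intervention attenders: a + τ
- All controls: (1 − p)a + p(a − d) = a − pd
- Per-protocol difference: **τ + pd**
- Difference between the arms as randomised: (1 − p)τ
- CACE: (1 − p)τ / (1 − p) = **τ**

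| p | d (mg) | Bias p × d (mg) | Share of 2.1 mg |
|---|---|---|---|
| any | 0 | 0 | 0% |
| 0.10 | 1.0 | 0.10 | 5% |
| 0.20 | 1.0 | 0.20 | 10% |
| 0.20 | 2.0 | 0.40 | 19% |
| 0.30 | 2.0 | 0.60 | 29% |

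**Simulation check** (101 per arm, SD 5.3 mg, baseline-adjusted, 4,000 runs per setting):
- No true effect, p = 0.3, d = 2.1: mean per-protocol estimate 0.62 mg, rejecting in 12.7% of runs (12.0% by formula). Two-stage least squares averaged −0.02 mg and rejected in 5.1%.
- τ = 2.1, p = 0.2, d = 2.1: per-protocol 2.52 mg, CACE 2.10 mg.
- τ = 2.1, p = 0.2, d = 0: both 2.11 mg, so there is no bias when d is zero.

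**Sessions analysis.** Take no true effect, p = 0.3 and d = 2.1. Simulated means against controls were −1.47 mg (no sessions), 0.63 mg (1–3) and 0.62 mg (4). Set would-be attenders' untreated mean at 0, so that non-attenders are at −2.1 and controls at −0.63. Attenders then differ from:
- all controls by 0.63 mg
- controls pooled with intervention non-attenders by (0.63 + 0.3 × 2.1) / 1.3 = 1.26 / 1.3 = 0.97 mg
- intervention non-attenders by 2.1 mg

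The SAP does not say which contrast is meant.

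**Price of CACE.** Its standard error is about 0.746 / (1 − p): 0.83 mg at p = 0.1, 0.93 mg at p = 0.2 and 1.07 mg at p = 0.3. Its power is about that of the comparison as randomised. With τ = 2.1, p = 0.2 and d = 2.1, the simulated rejection rates were 61.2% and 60.2%.

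**The case against.** The per-protocol analysis is a sensitivity analysis and the sessions analysis is exploratory. The primary analysis compares the arms as allocated in complete cases, with no attendance filter, and a multiple-imputation analysis of all randomised participants stands beside it. The definition is prespecified and commonly used, and controls have no sessions to attend. All of this stands, and it limits the weight of the point.

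Three stronger readings are tempting and are not supported.

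- *Both analyses are confounded and overstate benefit.* The SAP gives no attendance rate and nothing on untreated change by attendance. The bias is zero if d is zero, and its direction is plausible, not shown. Adjustment for baseline activity, gender and ethnicity may shrink d. If non-attenders are more often lost to follow-up, the effective p falls too. In the null illustration the no-session category came out negative, so overstatement does not describe every contrast.
- *Controls are pooled with intervention non-attenders in the lowest category.* That is one reading of section 4.5.2.3. Comparing each attendance group with all controls fits the text equally well. The supportable defect is that the reference group is not stated.
- *CACE settles the dose question from data in hand.* One binary instrument cannot separate the effect of 1–3 sessions from that of 4 without a further assumption. CACE also needs allocation to have no effect on non-attenders. Section 1.2.3 makes this plausible, since participants are invited "to receive regular reminders with Short Message Service (SMS) messages (text messages) after the first session", but the SAP does not say whether non-attenders get the messages. Missing outcomes need an assumption as well: the sample size allows for 20% loss to follow-up and 20% monitor non-compliance, and missingness related to attendance could bias CACE too.

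**Conclusion.** The point holds in limited form. The per-protocol rule selects on attendance in one arm only, and the sessions analysis compares self-selected groups against an unstated reference. Both are open to selection bias that the planned covariates need not remove.

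The per-protocol bias is p × d. For assumed p of 10–30% and d of 0–2 mg it is 0 to 0.6 mg, or 0–29% of the 2.1 mg target, probably but not certainly favouring the programme. The upper end needs 30% non-attendance and an untreated gap nearly as large as the target effect. At p = 0.2 and d = 1 the bias is 0.20 mg, about a quarter of the 0.746 mg standard error. A better method is available from allocation, attendance and outcome, which the planned analyses already require, so the change is worth making.

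**What to change.** 1. In sections 3.4 and 4.5.2.1, add as the main compliance-adjusted sensitivity analysis a CACE estimate by two-stage least squares. Randomised group is the instrument for attending at least one session, with the primary-model covariates.
2. State its assumptions: no effect of allocation on participants who attend no session (recording whether they receive text messages), no control access to the programme, and the assumption made about missing outcomes.
3. If the per-protocol analysis is kept, label it a non-randomised comparison.
4. In section 4.5.2.3, present the 0, 1–3 and 4 session categories descriptively within the intervention arm, without effect language. If a dose effect is wanted, use the session count (0 for controls) as the instrumented exposure and state that the effect is assumed linear in the number of sessions.

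The cost is SAP wording and one further Stata command, with no new data. The interval is wider: the standard error grows by a factor of about 1.11 at p = 0.1, 1.25 at p = 0.2 and 1.43 at p = 0.3, and there is no gain in power over the comparison as randomised.
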